Study design: The GLORIA study is a randomized, double-blind, placebo-controlled pragmatic multicenter clinical trial to assess the effectiveness and safety of a daily dose of 5 mg prednisolone or matching placebo in elderly RA patients. Patients will be randomized into two arms: the experimental arm (receiving prednisolone 5 mg/day) or the control arm (receiving placebo). Our design emulates the routine care setting: eligibility criteria are very liberal, assessments and procedures are tailored to represent standard of care, and concurrent antirheumatic treatment is allowed next to the trial medication with minimal limitations. Furthermore, all patients will have an adherence monitoring device loaded into the cap of the drug bottle; adherence data will be monitored throughout the trial. In addition, to test the effect of adherence reminders, a substudy (another trial) will be nested in the main GLORIA trial.

Substudy design: The substudy is limited to patients with a smartphone who have completed at least 3 months of the main study on treatment. The experimental arm of the substudy will receive an application loaded onto their smartphone that communicates with an adherence monitoring device loaded into the cap of the drug bottle and delivers reminders to improve adherence. The control arm of the substudy will not have this application and reminders. The substudy has a duration of three months.

Study population: Patients of 65 years of age and older with RA according to the 1987 or the 2010 classification criteria of the American College of Rheumatology (ACR) and the European League Against Rheumatism (EULAR), requiring antirheumatic therapy because of inadequate disease control, as evidenced

by a 28-joint disease activity score (DAS28) of ≥ 2.60 . For eligibility, the DAS28 can be calculated with ESR or CRP, and also recalculated from the DAS of 44 joints.

Substudy population: Patients in the main study who have completed at least 3 months on treatment, in possession of and familiar with a smartphone.

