5. STUDY DESIGN

The GLORIA study is a randomized, double-blind, placebo-controlled pragmatic multicenter clinical trial to assess the effectiveness and safety of a daily dose of 5 mg prednisolone or matching placebo in elderly RA patients.

Patients will be randomized into two arms: the experimental arm (receiving prednisolone 5 mg/day) or the control arm (receiving placebo). See chapter 7.1 for more details about the study medication. Treatment duration is two years.

Pragmatic trials are designed to evaluate the effectiveness of interventions in real-life routine practice conditions ([Schwartz D 1967](#)). Our design emulates the routine care setting: eligibility criteria are minimal, assessments and procedures are tailored to represent standard of care, and concurrent antirheumatic treatment is allowed next to the trial medication with minimal limitations. Thus we expect that almost all elderly RA patients (specifically those with comorbidities) are eligible.

The adherence of all patients in the main GLORIA trial is monitored throughout the study period by an adherence monitoring device loaded into the cap of the drug bottle. To measure the effect of smart reminders on medication adherence, a substudy (a randomized trial nested within the main study) will be performed. In this substudy, limited to patients with a smartphone, completing at least the first 3 months of the trial on treatment, the experimental arm will receive an application loaded onto their smartphone that communicates with the adherence monitoring device loaded into the cap of the drug bottle and delivers reminders to improve adherence. The control arm will not have this application and reminders. Intervention duration of the substudy is three months.

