6.3 Exclusion criteria

A potential subject who meets any of the following criteria will be excluded from participation in this study:

Lower probability of benefit:

- Change, stop or start of antirheumatic treatment in the last month prior to eligibility assessment, including methotrexate, sulfasalazine, hydroxychloroquine, leflunomide, azathioprine, intramuscular and oral gold, cyclosporine, biologic agents including anti-TNF, anakinra, abatacept, rituximab, tocilizumab (temporary exclusion);
- Treatment with systemic GC: oral or parenteral GC with a cumulative prednisolone equivalent dose of 200 mg or higher in the last 3 months (temporary exclusion);
- Treatment with any GC (oral, intra-articular, intravenous or intramuscular) in the last 30 days (temporary exclusion);
- Note: as this is a pragmatic trial, patients who require start of (other) antirheumatic treatment *at baseline or during the trial* can still be eligible (see 7.2).

Higher probability of harm:

- Exposure to investigational therapy in the last three months;
- Current participation in another clinical trial;
- Major surgery, donation or loss of approximately 500 ml blood within 4 weeks prior to the screening visit (temporary exclusion)
- Absolute contraindication to low-dose prednisolone, as determined by the treating physician, such as: uncontrolled chronic infections, diabetes mellitus, hypertension, osteoporosis. When these conditions are under control (e.g. with antiosteoporosis drugs, antihypertensive drugs) these patients can enter;
- Absolute contraindication to Calcium and/or Vitamin D supplement as determined by the treating physician, such as: hyperparathyroidism (when insufficiently treated);

- Uncontrolled comorbid conditions, short life span, etc. as determined by the treating physician.

Difficulty to measure harm/benefit:

- Absolute indication to start with oral or intravenous GC, according to the treating physician;
- Inability to comply with medical instructions or inability to assess major outcomes at 6-monthly visits, in the assessment of the treating physician.

Subjects/patients not capable or willing to provide informed consent.

Substudy

Additional exclusion criteria for subjects participating in the substudy to measure the effect of a reminder via smartphone on adherence:

Inability/difficulty to measure benefit:

- Not in the possession of a smartphone;
- Premature discontinuation of study medication within or at 3 months of the main trial.

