This adds power to the trial: we need only between 400 and 450 patients to detect the originally targeted contrast of 27,5%/20% = relative risk of 1,38 (Table 1).

At the expected pooled event rate of 40%, with 400 patients we have 80% power to detect a difference of 12% between placebo and prednisolone: i.e. placebo 34% and prednisolone 46%, a relative risk of 1,35. The results are better with 450 patients, and when the event rate is higher (Table 1).

At the moment of submission of the amendment trial recruitment has been closed on Dec 31, 2018 at a total of 452 patients.

Table 1. Sample size scenarios (one-sided alpha 5%).

expected event rate over 2 years		with power 80%,			
(% unique patients with at least one event)		detectable rate in predn group		Relative Risk	
pooled	placebo	n=400	n=450	n=400	n=450
30%	26%	38%	37%	1,47	1,43
35%	30%	42%	41%	1,40	1,37
40%	34%	46%	45%	1,35	1,32
45%	39%	52%	52%	1,31	1,31
50%	43%	55%	55%	1,28	1,28

For the substudy to measure adherence, no formal sample size calculation has been done. In feasibility assessments in the centres, the proportion of elderly patients with a smartphone was about 20%. However, in our current experience this is true only in the Netherlands. All other countries have indicated none of their currently included patients has a smartphone. Assuming that patients with a smartphone are technically interested, we can expect about 80% of them to be willing to participate. This gives a total sample size of 50 patients (25 per group). No data is available on actual adherence or its variability between patients.

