- Vital signs, height, weight, and abdominal circumference
- Bone mass assessed by Dual-energy X-ray Absorptiometry (DEXA).
- Vertebral Fracture Analysis (by DEXA OR lateral radiograph of thoracic and lumbar spine)
- Discontinuation of study drug with reason

This includes patients in whom treatment with prednisolone becomes clinically indicated or those with unacceptable side effects attributable to study medication;

- Change of antirheumatic treatment, with reason
- Intensification of treatment for existing comorbidity, e.g. hypertension or diabetes
- Joint replacement surgery

Data collection is in agreement with industry standard (i.e. Meddra terminology etc.)

b) Cost-effectiveness and cost-utility

Estimate of costs of treatment and monitoring, including prevention and treatment of side effects; out of pocket costs. Estimate of indirect costs based on activity limitations valued at shadow price; and work disability for those still holding a paid job. Resource use data will be obtained by a cost questionnaire completed three/six-monthly, medication use data will be collected with the eCRF, and the number of hospitalization days will be extracted from the narratives of the SAE forms.

c) Medication adherence

Adherence to trial drug is measured through the e-communicative packaging solution as the count of days in which the bottle is opened on the appropriate days, as measured by the adherence tool. The tool (cap) is collected at every study visit and replaced by a new specimen. Each cap (identified by study ID only) is sent back to the provider and the data are read out centrally. At the end of the study, the adherence data is added to the study database.

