All patients will be included in the cost-utility and cost-effectiveness analyses according to the intention-to-treat principle. Missing data will be imputed with multiple imputation by chained equations (with predictive mean matching). Stepwise linear and logistic regression analyses will be used to examine which variables are associated with missingness, and such variables will be included in the multiple imputation model. The data are imputed as total costs or utility score or DAS28 per time point per treatment arm (prednisolone or placebo). The imputed datasets will be bootstrapped with 5000 replications in order to estimate the uncertainty around the difference in costs and effects.

The imputed datasets will be bootstrapped with 5000 replications in order to estimate the uncertainty around the difference in costs and effects. The incremental Cost-Effectiveness and Cost-Utility Ratios (ICER and ICUR) will be calculated by dividing the difference between the mean costs per treatment group by the difference between the time-averaged disease activity per group and by the difference in QALYs per patient. The results will be graphically presented on a cost-effectiveness and cost-utility plane, and a cost-effectiveness acceptability curve will be constructed. This results in four different quadrants: two showing dominance of one treatment over the other, and two indicating a tradeoff between QALYs and costs.

Medication adherence

- Nonparametric and parametric comparisons between treatment groups where appropriate; one-sided significance levels ($\alpha=0.05$)
- Handling of premature discontinuations, dropouts and missing data: each patient will contribute until moment of discontinuation (weighted by total time in trial)

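### The protocol's adherence test does not specify adjustment for the cap adherence that each reminder-substudy patient should already have at substudy randomisation, and its weighting does not fit a 3-month comparison

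*Protocol*

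**What the plan says.** **Entry.** The Protocol Summary defines the substudy population as "Patients in the main study who have completed at least 3 months on treatment", with a smartphone. Section 5 repeats the rule ("In this substudy, limited to patients with a smartphone, completing at least the first 3 months of the trial on treatment"), and section 6.3 lists as an exclusion "Premature discontinuation of study medication within or at 3 months of the main trial".

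**Measurement.** Section 5 states: "The adherence of all patients in the main GLORIA trial is monitored throughout the study period by an adherence monitoring device". Section 9.1.1 c) defines adherence as a count of days with the bottle opened as scheduled, and adds: "The tool (cap) is collected at every study visit and replaced by a new specimen". SAP 1.4.1 names month 3 as one of the collection points.

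**Analysis.** Under Medication adherence, Protocol 11.1 gives two bullets. The first is "Nonparametric and parametric comparisons between treatment groups where appropriate; one-sided significance levels", at alpha 0.05. The second has each patient contribute until discontinuation, weighted by total time in the trial. Neither mentions earlier adherence. Section 9.2 stratifies substudy randomisation by country and study treatment, not by prior adherence. SAP sections 1 and 1.3.2 send the substudy analysis to a separate plan. SAP 4.13 lists main-trial adherence among outcomes to be reported descriptively.

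**Size.** Section 6.4 says that no formal calculation was done. It cites about 20% smartphone ownership, true only in the Netherlands, and continues: "All other countries have indicated none of their currently included patients has a smartphone". With about 80% willingness, it arrives at 50 patients, 25 per group.

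**The concern.** Testing whether smart-device reminders improve adherence is part of primary objective (b), yet the comparison has only about 25 patients per arm. The entry rule and the universal cap together supply a pre-randomisation value of the outcome at no cost, and such a value is usually the best available covariate. The protocol uses this principle for DAS28, where the model in 11.1 includes the baseline value. For adherence it states nothing comparable.

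The weighting raises a second problem. A weight equal to total time in the trial suits adherence measured over the whole study. Applied to a 3-month comparison that starts at month 3 or later, it would give patients different weights for reasons unrelated to how much substudy data they contribute.

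At stake are the sensitivity of a small test and the avoidance of a post-hoc choice of covariate, window and weight. The main trial's conclusions are not affected.

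**Working it through.** **1. Does a pre-randomisation value exist?** Entry requires at least 3 months on treatment (Protocol 1, 5, 6.3). The cap is used by all patients throughout (Protocol 5) and collected at study visits (Protocol 9.1.1), including month 3 (SAP 1.4.1). Barring cap failure, each substudy patient has about 3 months or more of cap data before substudy randomisation.

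**2. Weighting.** Suppose, for illustration, that one patient enters the substudy at month 3 and another at month 12, and both complete it. Each contributes 3 months of outcome. Counting time in the trial to the end of the substudy, the weights would be 3 + 3 = 6 months and 12 + 3 = 15 months, a ratio of 2.5 for the same amount of substudy data. Weighting by substudy time gives 3 and 3.

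**3. Detectable difference.** The plan gives no figure to reproduce. Inputs from the documents are 25 per arm (6.4) and one-sided alpha 0.05 (11.1). Power of 80% is assumed, as is the correlation r between adherence before and after randomisation, because 6.4 says that no adherence data were available. In SD units:

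d = (1.645 + 0.842) × √(2/25) × √(1 − r²) = 0.703 × √(1 − r²)

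| r (assumed) | variance removed, r² | d, 80% power | power for 0.5 SD |
|---|---|---|---|
| 0 (unadjusted) | 0% | 0.70 | 55% |
| 0.3 | 9% | 0.67 | 58% |
| 0.5 | 25% | 0.61 | 65% |
| 0.7 | 49% | 0.50 | 80% |
| 0.8 | 64% | 0.42 | 90% |

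The normal approximation is adequate: a t-based calculation gives 0.71 in place of 0.70 for the unadjusted case.

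**4. The expected 50.** From 6.4, 0.20 × 0.80 = 0.16. Applied to all 452 recruited patients this gives 452 × 0.16 = 72, not 50. Applied to the Netherlands only, as the text requires, 50 needs 50/0.16 = 312.5, so 313 Dutch patients, or 313/452 = 69% of the trial. Both percentages are approximate: ownership of 15% to 25% at 80% willingness moves the requirement from 417 to 250. Dutch enrolment is not given. As an assumption, 100 to 250 Dutch patients would yield 16 to 40 participants.

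**The case against.** The strongest objection is that the bullet in 11.1 may not be the substudy analysis at all. It sits under a heading covering an outcome measured in everyone, speaks of treatment groups, and mentions neither the app nor reminders. Section 9.2 uses treatment for the study drug, as distinct from having the application. Weighting by total time is natural for prednisolone versus placebo over the whole trial. The substudy analysis is expressly deferred to another plan, which may already adjust.

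This stands in part. A reader might infer that the plan prescribes an unadjusted substudy comparison or discards the run-in data. The documents do not show that: the bullet is generic, allows methods as appropriate and does not exclude ANCOVA. What remains is that no supplied document specifies a test for this part of a primary objective beyond that bullet, and that its weighting would be unsuitable if carried over.

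A reader might also infer that most of the precision is lost without adjustment. That depends on an unknown correlation: half the variance is removed only when r exceeds about 0.7.

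On size, a reader might infer that 50 is wrong or unattainable, or that randomisation depends on it. Neither follows. It is a feasibility count with no power claim attached, the Dutch denominator is missing, and minimisation (9.2) allocates sequentially without needing a fixed total.

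**Conclusion.** The point holds as an inexpensive improvement, not as a demonstrated error. Cap adherence before substudy randomisation should exist for each substudy patient, and the only adherence test supplied does not specify its use. If that test's weighting were applied to the 3-month substudy, it would count time before randomisation.

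Adjustment would lower the detectable difference at 25 per arm from 0.70 SD to between 0.67 and 0.42 SD for correlations of 0.3 to 0.8. These correlations are assumed, and the figures treat adherence as roughly normal; a bounded, skewed percentage would call for a rank-based version. If the separate plan already adjusts and limits the window and weights to the substudy, a cross-reference from 11.1 is enough.

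The size remark is secondary. The stated 50 does not follow from the stated percentages without a Dutch denominator, and nothing in the documents shows whether that denominator is large enough.

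**What to change.** In Protocol 11.1 and the adherence analysis plan, state separately for the substudy:

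- **Outcome:** cap adherence over the 3 substudy months.
- **Analysis:** ANCOVA comparing reminders with no reminders, or rank-ANCOVA if the distribution is skewed, adjusted for cap adherence in the 3 months before substudy randomisation.
- **Weighting:** time in the substudy, replacing total time in the trial.

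Say in 11.1 whether the existing bullets apply to prednisolone versus placebo, to the substudy, or to both. In 6.4, restate the expected size as Dutch patients on treatment at 3 months × 0.16, and carry the result into 9.2.

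The cost is wording only, since the cap data are already collected; the analyst should confirm that the read-outs can be divided at the date of substudy randomisation. The restated expected size may be below 50. The covariate, window and weights should be fixed before substudy results are seen.

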11.2 Secondary study outcome(s)

For continuous variables, (e.g. RA core, SF36, RAID, QALY) first univariate analyses will be conducted to evaluate their distributions and the presence of outliers. If the variables are not normally distributed they will be transformed. Then mixed regression models will be used to study changes in their levels over the follow-up.

For categorical variables (e.g. ACR response, EULAR response) multiple exclusive groups will be defined and differences between the intervention and control groups will be tested by a chi-squared test for linear-by-linear association. In secondary analyses, generalized linear mixed models (GLMM) will be used to assess different

patterns of change during the follow-up. Finally, number needed to treat and number needed to harm analyses will be conducted on selected categorical variables based on the observed events in the placebo group.

12. ETHICAL CONSIDERATIONS

12.1 Regulation statement

The study will be conducted according to the principles of the Declaration of Helsinki (64th WMA General Assembly, Fortaleza, Brazil, October 2013, see for the most recent version: www.wma.net), GCP and in accordance with the Medical Research Involving Human Subjects Act (WMO) and other guidelines, regulations, and Acts.

12.2 Recruitment and consent

Subjects will be recruited from the investigational sites based on the eligibility criteria provided in the protocol. They will be informed about the study by their treating rheumatologist, where after they receive the patient information letter and the researcher or research nurse will provide extra information on request. Subjects can think about participation as long as needed.

Voluntary written Informed Consent Form (ICF) must be obtained from each subject prior to performing any study related procedures in compliance with the recommendations of the Declaration of Helsinki. Subjects should not be screened or study drug administered until the subject has signed an approved ICF written in a language that is understandable to the subject.

Each subject should be given both verbal and written information describing the nature and duration of the clinical study. The ICF should be signed and personally dated in two originals by the subject and the person who conducted the informed consent discussion. The Investigator, or the attending health care professional will explain the nature, purpose and risks of the study. The subject will be informed that he/she has the right to withdraw at any time from the study, without giving reasons. In this condition, the subject will also be informed that he/she will not receive any indemnity. The informed consent process should take place under conditions where the subject has adequate time to consider the risks and benefits associated with his/her participation in the study.

Each subject should receive one original of the signed and dated written ICF and any other information provided to the subject. The second original of the signed and dated ICF should be retained in the investigator's file. The investigator should maintain a log of all subjects who sign the ICF.

12.3 Benefits and risks assessment, group relatedness

Since GLORIA is a pragmatic trial, it is designed to evaluate the effectiveness of interventions in real-life routine practice conditions. This means almost all measurements are part of standard of care, and therefore there are no additional risks associated with these measurements.

However, the intervention in this trial is that patients are randomised to either standard of care with low-dose GCs or standard of care with matching placebo for a duration of two years. It is known that GCs have strong favourable effects on disease activity, however, side effects are known as well, predominantly when used in

high-doses and for a long period of time. Unfortunately, clinical studies large enough to adequately document the balance between benefit and harm of low-dose GCs in combination with standard of care are lacking. And although elderly patients are overrepresented in terms of patient numbers in RA, this group exemplifies the challenge that they are underrepresented or even excluded from many clinical trials that generate the evidence-base for treatment of RA. However, the limited high-quality data from trials does not support strong claims of harm, but the generalizability of trial data is questioned. Therefore, the primary objective of the GLORIA trial is to deliver evidence-based information on the GC harm/benefit balance.

For the substudy to measure adherence, no additional risks are expected. Non-adherence substantially increases the risk of a disease flare in RA. GLORIA measures adherence through a medication packaging device and tests an innovative application to improve medication adherence in elderly patients. If this application appears to be successful, patients randomised to this intervention can only benefit from it since it improves their medication adherence. In case the application is not successful, or patients are not randomised to the application, or for patients without a smartphone, no difference is expected with the 'normal' situation, in which patients do not have access to an adherence application. Furthermore, results of adherence monitoring and a positive result of the adherence intervention will have a large impact in the elderly population as a whole, and even more in the younger population where the penetration of smartphones is so much greater.

